6.1 CE-CBBCT PROCEDURE

The subjects will first have a pre-contrast CBBCT scan. Iodinated contrast will be injected intravenously, and then another CBBCT scans will be performed to capture the tumor vasculature enhancement. Features to look for are degree of enhancement pattern of the lesion as compared to surrounding pattern. Delay times and contrast volume/rate will be determined initially through previous CT studies then optimized through this CBBCT study. Each CBBCT scan takes 10 seconds and delivers a glandular dose similar to a diagnostic mammography exam. State board-certified and Mammography Quality Standards Act (MQSA) qualified mammographers will evaluate the CBBCT high resolution 3D images and compare them to the subjects' mammograms. If the subject had an MRI or ultrasound, then these would be compared as well. If the patient's diagnostic outcome is BIRADS 4 and above and has biopsy or surgery, pathology will provide final confirmation. If the patient's diagnostic outcome is BIRADS 1, 2, 3, follow up results will provide final confirmation.

Physicians familiar with contrast-enhanced multislice CT procedures will be available during the CE-CBBCT procedures and will advise on modifications.

Once all the projections are acquired, projections will then be used for volume reconstruction. Since a malignant tumor has many blood vessels, it will be enhanced in the post-contrast reconstructed image. The contrast enhancement of the malignant tumor will be quantified by CT number measurements. To explore dynamic contrast-enhanced vasculature patterns (wash-in, wash-out), we propose to select the scan at various delay times on different subjects with similar lesions to see if we can get preliminary data on this functional effect while keeping the dose to individual subjects low.

The radiographic technique will be 49 kVp, 8 ms/projection image, and 300 images per scan. The mA will be automatically selected by the CBBCT system from 50 to 160 mA, depending on size and density of the breast. This translates to a range of average glandular dose to the breast from ~4

Clinical Trial Protocol			
Title:	Contrast-Enhanced Cone Beam Breast CT for Diagnostic Breast Imaging		
Internal #:	16-01		
IRB #:	RSRB00061893	NCT #:	NCT03354611
Revision:	3.5	Effective Date:	

mGy to ~13 mGy per scan, depending on breast size and density, or similar to the subject's diagnostic mammogram. In this study, the dose for a full two-scan contrast imaging will be ~ 8 to 32 mGy, or similar to two diagnostic mammography exams.

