6.3 CE-CBBCT EVALUATION

6.3.1 Dose Considerations:

For iodinated contrast studies of the breast, we propose to initially perform a pre-contrast scan and 1 post-contrast scan. Exact timing of the post-contrast scans needs to be explored as part of this study. The average glandular dose to the breast volume per scan will be 4 mGy to 13 mGy per scan (+/-20%), depending on breast size and density or similar to the subject's diagnostic mammogram. Thus, the dose for a full two-scan protocol will be ~ 8 to 26 mGy, or similar to two diagnostic mammography exams.

By comparison, this dose is up to 2-3 times lower than multi-slice CT scans of the breast, which results in a $CTDI_{100} \sim 12-18$ mGy glandular dose/scan. In addition, these multi-slice CT scans radiate the entire thorax in addition to the breast at much higher photon energies (120 kVp compared to 49 kVp). The effective dose from a conventional chest CT scan is 7 mSv, which is equivalent to 2 years of natural background radiation [16]. The effective dose from a two-scan, single breast CE-CBBCT exam is from 0.12 mSv to 3.8 mSv, which is equivalent to approximately 4.6 months to 14.7 months of natural background radiation. This conversion is based on a breast tissue weighting factor of 0.15 per NRC 10CFR 20.1003 Definitions.

Two scans are typically performed at ~30 seconds and 2 minutes after contrast injection. In addition, 3 mm thick slices are taken to scan the breast volume. At 0.8 sec/rotation and a pitch of 1, it takes ~40 seconds to cover ~150 mm distance to capture the full breast. Contrast enhancement can change significantly during this time. The CBBCT scan, however, takes only 10 seconds to scan a full breast volume thus capturing a volume "snapshot" of the contrast-enhanced tumors at that time.

6.3.2 Image Processing:

CE-CBBCT scans will be reconstructed to maximize dynamic enhancement data. The various time-dependent reconstructions and approaches will be tested and evaluated to determine the optimized time delay after contrast injection before start of the scan.

Clinical Trial Protocol			
Title:	Contrast-Enhanced Cone Beam Breast CT for Diagnostic Breast Imaging		
Internal #:	16-01		
IRB #:	RSRB00061893	NCT #:	NCT03354611
Revision:	3.5	Effective Date:	

6.3.3 Review of the CE-CBBCT:

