Analysis based on data from 220 diagnostic patients, which are representative of the range of breast thicknesses and densities found in a female population, has shown that the average mean glandular dose of one CBBCT scan and one diagnostic mammography exam is 10.6 mGy (standard deviation 3.89) and 9.57 mGy (standard deviation 5.16), respectively. The overall dose range is comparable and the dose values are less variable for the CBBCT [14].

The CBBCT study includes two low dose scout images, acquired at a standard dose (~0.30 each for the two images; 0.6 mGy total), and the CBBCT scan. For the CBBCT scan, we propose delivering the *minimal* average glandular dose level required to maintain sufficient image quality for each subject. The dose from the CBBCT scan varies with breast size and density and is determined for each individual breast from the two low-dose scout images. Dose from the CBBCT scan will range from ~4 mGy to no more than ~16 mGy (+/- 20%) (depending on breast size and density) to provide a CNR of ~8, the level needed for diagnostic adequacy. The amount of radiation exposure from one CBBCT scan of one breast is equivalent to an effective whole body dose of ~0.6 - 1.9 mSv. Thus, the highest dose from the CBBCT of 1.9 mSv would approximate the same dose received from about 7

Clinical Trial Protocol			
Title:	Contrast-Enhanced Cone Beam Breast CT for Diagnostic Breast Imaging		
Internal #:	16-01		
IRB #:	RSRB00061893	NCT #:	NCT03354611
Revision:	3.5	Effective Date:	

½ months of background radiation. The CBBCT dose is within the range of what could be expected from diagnostic mammography studies.

The dose range of the CBBCT study is substantially less than the minimum dose recognized to induce an increased risk for breast cancer. In addition, we will institute a data safety and monitoring plan for this study to assure that dose remains within the stated limits, while continuously evaluating image quality along with improvements that may reduce the dose of the CBBCT study.

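### Sections 6 and 12 give different upper radiation doses, Section 6.1 mixes the two sets, and the upper effective doses in Section 12.2 do not follow from its own figures

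*Protocol*

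**What the plan says.** The dose figures appear in five places in the current protocol.

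- **Section 6.1:** from about 4 "mGy to ~13 mGy per scan, depending on breast size and density". The next sentence says "the dose for a full two-scan contrast imaging will be ~ 8 to 32 mGy".
- **Section 6.3.1:** "The average glandular dose to the breast volume per scan will be 4 mGy to 13 mGy per scan (+/-20" (percent), and for the exam "the dose for a full two-scan protocol will be ~ 8 to 26 mGy". The effective dose for a "single breast CE-CBBCT exam is from 0.12 mSv to 3.8 mSv", equated to 4.6 to 14.7 months of natural background, using a breast weighting factor of 0.15.
- **Section 12.2:** "Dose from the CBBCT scan will range from ~4 mGy to no more than ~16 mGy (+/- 20" (percent). One scan is "equivalent to an effective whole body dose of ~0.6 - 1.9 mSv". The two-scan exam is put at about 8 to 32 mGy, again ±20%, and at 1.2 to 3.8 mSv or 4.6 to 14.7 months, with the factor of 0.15 stated for the exam.
- **Section 12.4:** 4 to 16 mGy for a repeated scan, and 12 to 48 mGy in total after a machine failure.
- **Section 1.2:** an 11.6 mGy exam converted to 1.39 mSv with a factor of 0.12.

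Section 12.2 commits to a monitoring plan "to assure that dose remains within the stated limits". Section 13 repeats the commitment without a number. It also requires an annual report comparing the dose actually used with the estimates in the radiation committee application.

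**The concern.** Section 12.2 says dose rises linearly with the number of scans, so each per-scan value fixes its exam value. On that rule the document carries two sets of upper values, 13/26 mGy and 16/32/48 mGy, and Section 6.1 takes its per-scan figure from one and its exam figure from the other. Separately, Section 12.2 converts mGy to mSv in a way that no single factor reproduces.

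The protocol relies on these figures. Section 12 is the risk statement for the study radiation, and the monitoring plan refers to stated limits that can only be read from Section 6 or Section 12. A scan at, say, 17 mGy would lie outside the Section 6.3.1 range with its tolerance (15.6) and inside the Section 12.2 range with its tolerance (19.2). Whether it counted as a breach would depend on the section consulted.

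**Working it through.** **Inputs.** Per-scan ranges of 4 to 13 mGy (Sections 6.1, 6.3.1) and 4 to 16 mGy (Sections 12.2, 12.4); tolerance ±20% (Sections 6.3.1, 12.2); factor 0.15 (Sections 6.3.1, 12.2) or 0.12 (Section 1.2); linear scaling with number of scans (Section 12.2).

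**Formulas.** Exam dose = 2 × per-scan dose. Machine-failure dose = 3 × per-scan dose. Effective dose (mSv) = glandular dose (mGy) × weighting factor.

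**Step 1: figures that reproduce.** 2 × 4 = 8; 2 × 13 = 26 (Section 6.3.1); 2 × 16 = 32 (Section 12.2); 3 × 4 = 12 and 3 × 16 = 48 (Section 12.4). Sections 6.3.1 and 12 are each consistent within themselves on mGy.

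**Step 2: Section 6.1.** 2 × 13 = 26, not 32. The stated 32 is 2 × 16.

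**Step 3: size of the conflict.**

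| | Based on 13 | Based on 16 | 13-based, +20% | 16-based, +20% |
|---|---|---|---|---|
| Scan (mGy) | 13 | 16 | 15.6 | 19.2 |
| Exam (mGy) | 26 | 32 | 31.2 | 38.4 |
| Machine failure (mGy) | 39 | 48 | 46.8 | 57.6 |

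The ratio is 16/13 = 1.23 in every row. The protocol does not state 39; it is 3 × 13. Section 12.4 attaches no tolerance, so 46.8 and 57.6 apply the same 20% by assumption.

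**Step 4: can the sets be reconciled?**
- Tolerance: 26 × 1.2 = 31.2 is near 32. But the lower end in Section 6.1 stays at 8 rather than 8 × 0.8 = 6.4, and Section 12.2 applies ±20% on top of 16 and 32.
- Scout images: Section 12.2 gives 0.6 mGy in total. 13 + 0.6 = 13.6, not 16.
- Rounding cannot turn 13 into 16 or 26 into 32.

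**Step 5: effective dose in Section 12.2.**

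| mGy | Stated mSv | Implied factor | At 0.15 | At 0.12 |
|---|---|---|---|---|
| 4 (scan) | 0.6 | 0.150 | 0.6 | 0.48 |
| 16 (scan) | 1.9 | 0.119 | 2.4 | 1.92 |
| 8 (exam) | 1.2 | 0.150 | 1.2 | 0.96 |
| 32 (exam) | 3.8 | 0.119 | 4.8 | 3.84 |

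The factor 0.15 fits only the lower ends and 0.12 only the upper ends. At 0.15 the upper products exceed the stated values by 26% (4.8/3.8 = 2.4/1.9 = 1.26). Read the other way, 3.8/0.15 = 25.3 mGy, not 32.

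**Step 6: background months.** Section 12.2 implies 1.2/4.6 = 0.261 and 3.8/14.7 = 0.259 mSv per month. At those rates 4.8 mSv is 18.4 to 18.6 months, against 14.7 stated.

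**Step 7: smaller points.**
- Section 6.3.1, upper end: 26 × 0.15 = 3.9, close to the stated 3.8 (3.8/26 = 0.146). This is not part of the problem.
- Section 6.3.1, lower end: 8 × 0.15 = 1.2 mSv, ten times the stated 0.12. At about 0.26 mSv per month, 0.12 mSv is roughly 0.5 month, not the 4.6 given beside it.
- Section 1.2: 11.6 × 0.12 = 1.39, as stated; at 0.15 it would be 1.74 mSv.

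**The case against.** None of these figures sets a woman's exposure. The system selects the mA from scout images, the current text has a single mA range (50 to 160), and the investigator reviews the technique used for each subject. Most values carry an approximation sign, and Section 6 describes an expected range, whereas Section 12.2 uses the language of a maximum. The 17 mGy scan is hypothetical: Section 6.1 says the mA range yields about 4 to 13 mGy. The annual comparison is against an application not shown, so harm to monitoring is unproven. Finally, the two main parts may have one cause: at 0.15, 13 mGy gives 1.95 mSv and 26 mGy gives 3.9, close to the 1.9 and 3.8 in Section 12.2, so the mSv gap would close if the 13/26 set were adopted throughout.

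Much of this stands. The 4.8 mSv and 18.5 months arise only if 16 and 32 mGy are kept, so they do not establish that risk is understated. The 0.15 is stated for the exam; for the single scan it is inferred from 4 mGy giving 0.6 mSv. The factor in Section 1.2 is declared and consistent with its own result, so that is a difference of convention.

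None of it removes the contradiction. Automatic mA selection does not tell a monitor which stated limit applies, and a possible common cause does not correct the text.

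**Conclusion.** The contradiction is real and should be corrected. The current protocol carries two sets of upper doses that differ by 23%, and Section 6.1 combines them. In Section 12.2 the upper mGy and mSv figures cannot both hold at 0.15. If the mGy values are kept, the upper effective doses rise by 26%, to 2.4 and 4.8 mSv; if the mSv values are kept, the exam maximum is about 25.3 mGy. This rests only on the stated figures, linearity in the number of scans, and conversion by one factor. It does not rest on the revision history.

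The consequence is limited to the monitored dose limit and the risk statement. Endpoints and analysis are untouched. Even 48 mGy plus an assumed 20% is 57.6 mGy, well below the 200 mGy cited in Section 12.2. The ten-fold slip in Section 6.3.1 and the differing factor in Section 1.2 are minor. Which set is right cannot be judged from the protocol, and no view is taken.

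**What to change.** The sponsor and the radiation physicist should reconcile Sections 1.2, 6.1, 6.3.1, 12.2 and 12.4:

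1. Adopt one per-scan range, one two-scan range and one machine-failure range, and say once whether the ±20% applies to each.
2. Adopt one weighting factor, and recompute every mSv and background-month figure from it.
3. Correct the 0.12 mSv in Section 6.3.1.
4. Check the result against the radiation committee application and any subject-facing text that repeats the figures.
5. State in Section 13 the numerical limit being monitored.

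The choice of values belongs to the sponsor. The cost is a text correction and that check; procedures, endpoints and analysis do not change.

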6.2 CE-CBBCT TECHNICAL DETAILS

6.2.1 CBBCT for Breast Imaging System:

The CBBCT system employs a horizontally oriented gantry beneath a subject support table, which incorporates an x-ray tube with a 0.3 mm focal spot at one end and a high-resolution, 40 x 30 cm real-time flat panel detector (FPD) at the opposite end. The extensive detector dynamic range (>16 bit) along with the 3D imaging technique provides up to 30x greater contrast resolution than standard imaging. The system is designed and built in compliance with the national and international safety standards for medical equipment.

For a CBBCT scan, the subject lies prone on the support table. The breast of interest is placed through the opening in the table and the breast is positioned in the imaging field. The table sits above a motorized scanning arm carrying an x-ray source and image detector that allows a 360° rotational x-ray sequence in ~10 seconds. To acquire the 10 second, full-volume scan of the breast, the CBBCT gantry rotates 360° around the subject's breast, acquiring 300 pulsed projection images at ~8 ms each. Acquired image data is sent to a computer to perform 3D reconstruction. Specialized 3D visualization software constructs a three-dimensional model of the breast from the images taken during the rotational x-ray sequence. Once the data is reconstructed, it provides the radiologist with $(0.27 \text{ mm})^3$ (standard resolution) cross-sectional slice data displayed in any plane as well as a 3D rendering. The data set can be reconstructed to $(0.155 \text{ mm})^3$ with a sharp ramp filter for high resolution volume of interest (especially for calcifications) without having to re-scan the subject.

Our previous studies to-date has illustrated the capacity of the non-contrast CBBCT to image the breast without structure overlap and with superior contrast resolution as compared with standard breast imaging. The study results illustrate that the CBBCT system is able to image the entire breast from axillary region to chest wall with clinically acceptable image quality and radiation dose comparable to conventional mammography. Cancers are better visualized as well as defined. In general, it is observed, that cancerous tissues absorb more x-rays than normal tissues, as determined by a higher Hounsfield unit, (CT number or x-ray attenuation coefficient), but the CT number of some benign entities can match that of cancer.

6.2.2 Subject Positioning and Image Acquisition:

A unilateral 3D CE-CBBCT for breast imaging study will be performed. After intravenous access is accomplished, the subject will be placed on the imaging table in the prone position in a left or right anterior oblique position so that the breast of interest suspends through the table opening into the volume of image acquisition. A radiologic technologist, registered in radiography and

Clinical Trial Protocol			
Title:	Contrast-Enhanced Cone Beam Breast CT for Diagnostic Breast Imaging		
Internal #:	16-01		
IRB #:	RSRB00061893	NCT #:	NCT03354611
Revision:	3.5	Effective Date:	

mammography through the ARRT and who is also trained in 3D CE-CBBCT acquisition, will position the breast and acquire the images.

6.2.3 Pre-study Screening:

As per department protocol, subjects will undergo pre-study screening (including POCT and serum eGFR as indicated) to avoid contrast reaction and toxicity. If there are any potential contraindications to the use of contrast with a study subject, the subject will be excluded. (Appendices A, B, C)

6.2.4 Contrast Injection:

A nurse, trained in intravenous contrast injections and reactions, will establish intravenous access through a peripheral vein using a catheter. The arm opposite of the breast to be scanned will be used to administer the IV contrast to reduce the chance of the contrast directly entering the veins of the scanned breast. The nurse will be present through the study. A physician will supervise the injections. A clinically certified power injector will be used to deliver a bolus injection. As a starting point, 1.5-2ml/kg body weight (100 ml maximum) of a low osmolar, nonionic, 300-350 mgI/ml iodinated contrast agent, will be injected at a rate of ~2.0 ml/s, for a total injection time of 30-60 seconds (for a 50 kg subject). This will be immediately followed by a saline "chaser" from 20 to 40 ml at ~2 ml/s (20 seconds) to maximize dynamic enhancement. A bolus test with small amount of contrast to determine the timing of the particular subject's peak enhancement could be performed using a series of low dose pulsed scout images. (Appendices D, E, F)

For those subjects who are found to have limited IV access, hand injection will be used to deliver the contrast agent. Using the same formula of 2ml/kg body weight, up to 100ml of low osmolar, nonionic 300-350 mgI/ml iodinated contrast agent will be injected over 30-60 seconds. This will be followed by a 20 to 40ml saline bolus delivered also by hand injection.

6.2.5 Contrast-enhanced Scan Protocol:

For iodinated contrast studies of the breast, we propose to initially perform a pre-contrast scan and one post-contrast scans. Exact timing of the post-contrast scans needs to be explored as part of this study. As a starting point:

- Pre-contrast scan
- Begin contrast injection (and saline chaser)
- Start time of post-contrast CE-CBBCT scan is 90-200 seconds after start of injection, depending on method of contrast delivery (bolus vs hand injection)

Clinical Trial Protocol			
Title:	Contrast-Enhanced Cone Beam Breast CT for Diagnostic Breast Imaging		
Internal #:	16-01		
IRB #:	RSRB00061893	NCT #:	NCT03354611
Revision:	3.5	Effective Date:	

6.2.6 Power Injector:

A power injection system will be utilized. If a power injector is not available, hand injection by a certified physician or nurse is also acceptable.

6.2.7 Post-study Monitoring:

We will observe department protocol for patient follow-up after IV contrast injection.

6.3 CE-CBBCT EVALUATION

6.3.1 Dose Considerations:

For iodinated contrast studies of the breast, we propose to initially perform a pre-contrast scan and 1 post-contrast scan. Exact timing of the post-contrast scans needs to be explored as part of this study. The average glandular dose to the breast volume per scan will be 4 mGy to 13 mGy per scan (+/-20%), depending on breast size and density or similar to the subject's diagnostic mammogram. Thus, the dose for a full two-scan protocol will be ~ 8 to 26 mGy, or similar to two diagnostic mammography exams.

By comparison, this dose is up to 2-3 times lower than multi-slice CT scans of the breast, which results in a $CTDI_{100} \sim 12-18$ mGy glandular dose/scan. In addition, these multi-slice CT scans radiate the entire thorax in addition to the breast at much higher photon energies (120 kVp compared to 49 kVp). The effective dose from a conventional chest CT scan is 7 mSv, which is equivalent to 2 years of natural background radiation [16]. The effective dose from a two-scan, single breast CE-CBBCT exam is from 0.12 mSv to 3.8 mSv, which is equivalent to approximately 4.6 months to 14.7 months of natural background radiation. This conversion is based on a breast tissue weighting factor of 0.15 per NRC 10CFR 20.1003 Definitions.

Two scans are typically performed at ~30 seconds and 2 minutes after contrast injection. In addition, 3 mm thick slices are taken to scan the breast volume. At 0.8 sec/rotation and a pitch of 1, it takes ~40 seconds to cover ~150 mm distance to capture the full breast. Contrast enhancement can change significantly during this time. The CBBCT scan, however, takes only 10 seconds to scan a full breast volume thus capturing a volume "snapshot" of the contrast-enhanced tumors at that time.

6.3.2 Image Processing:

CE-CBBCT scans will be reconstructed to maximize dynamic enhancement data. The various time-dependent reconstructions and approaches will be tested and evaluated to determine the optimized time delay after contrast injection before start of the scan.

Clinical Trial Protocol			
Title:	Contrast-Enhanced Cone Beam Breast CT for Diagnostic Breast Imaging		
Internal #:	16-01		
IRB #:	RSRB00061893	NCT #:	NCT03354611
Revision:	3.5	Effective Date:	

6.3.3 Review of the CE-CBBCT:

Two MQSA qualified board-certified mammography radiologists will evaluate the CE-CBBCT study along with all prior imaging and histological results to determine the added value of CE-CBBCT. Initially, the radiologists will review the CE-CBBCT images and make independent diagnostic decisions blindly from MRI and ultrasound image results, if available. Next, they will compare the results of CE-CBBCT to diagnostic mammography, non-contrast CBBCT, MRI, and ultrasound images. Finally, they will compare their findings for each case to histological results, which are considered to be the quantitatively gold standard in diagnosis. The comparison will answer three questions:

1. Can the CE-CBBCT detect lesions that not detected by other modalities?
2. Can the CE-CBBCT better distinguish between benign and malignant masses?
3. Can the CE-CBBCT help show the extent of disease?

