5.7 INCLUSION CRITERIA

- Female sex
- Age 35 years or older
- Any ethnicity
- Have an abnormality detected by Breast Self Exam (BSE), or Clinical Breast Exam (CBE), or have an abnormality detected by an imaging modality.
- Will undergo study imaging within four weeks from the date of diagnostic mammography, prior to breast biopsy (if needed).
- Able to provide informed consent
- Post-menopausal, surgically sterile, or effective birth control. For women of childbearing potential, negative pregnancy test or has signed pregnancy test waiver
- If required by standard of care, eGFR \geq 45 within 48 hours to 6 weeks of CE-CBBCT exam

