8 DATA COLLECTION

The following represents source documentation for data to be collected:

- Original mammogram OR reasonable quality copies of the subject's mammogram
- CE-CBBCT images
- Ultrasound images (if any)
- MR images (if any)
- CRF 1-6
- CRF 7-10 as appropriate
- Physicians Reports if performed for:

Clinical Trial Protocol			
Title:	Contrast-Enhanced Cone Beam Breast CT for Diagnostic Breast Imaging		
Internal #:	16-01		
IRB #:	RSRB00061893	NCT #:	NCT03354611
Revision:	3.5	Effective Date:	

- Mammogram
- Ultrasound
- Breast MRI
- Pathology Reports
- Definitive Surgery

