9 ANALYSIS OF RESULTS

All data will be collected in a spreadsheet.

Contrast-enhanced CBBCT (CE-CBBCT) for breast imaging will be evaluated, tabulated, and analyzed in terms of lesion conspicuity and detail in comparison with the non-contrast CBBCT exam, mammogram, and contrast-enhanced breast MRI. We will evaluate wash in and wash out patterns and degree of enhancement of the lesion as compared to surrounding pattern.

Demographic and clinical characteristics of the study population will be described using mean and standard deviation for quantitative variables such as age, or percentage and percentiles for qualitative variables such gender, race, and cancer staging.

Reported adverse events will be tabulated according to its description, severity, and relationship to the specific imaging or clinical procedures. All patients will be included in the safety analysis.

Paired t-test (for quantitative measurements such as tumor size, time of wash in and wash out) or McNemar's test (for qualitative data such as type of mass, type of calcification) will be used for comparisons between the CE-CBBCT and other modalities.

Accuracy of diagnosis will be evaluated in terms of sensitivity and specificity by comparing the test results from each imaging modality to that of the biopsy (the gold standard). When sufficient data is available, comparisons between CE-CBBCT and the other modalities will then be conducted using McNemar's test.

No imputation will be used for missing data (i.e., only patients who have the specific data available will be included in a particular analysis.) Statistical analysis will be performed using SAS (SAS Institute, Cary, N.C., U.S.A.). All tests will be 2-sided with the confidence level set to 95%.

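### Section 6.3.3 masks the first CE-CBBCT decision expressly to MRI and ultrasound only, so the conditional accuracy comparison with diagnostic mammography in Section 9 is open to review bias of unknown direction and size

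*Protocol*

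**What the plan says.** Protocol Section 6.3.3 sets out the reading in three steps.

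1. The readers review the CE-CBBCT images and "make independent diagnostic decisions blindly from MRI and ultrasound image results, if available".
2. "Next, they will compare the results of CE-CBBCT to diagnostic mammography, non-contrast CBBCT, MRI, and ultrasound images".
3. "Finally, they will compare their findings for each case to histological results".

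The opening sentence of the same section is broader. It has the two radiologists evaluate CE-CBBCT together with all earlier imaging and the histology, and it gives no order and no exception.

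Section 6.1 also describes a reading: "mammographers will evaluate the CBBCT high resolution 3D images and compare them to the subjects' mammograms". It states neither masking nor sequence.

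Section 9 assesses CE-CBBCT "in comparison with the non-contrast CBBCT exam, mammogram, and contrast-enhanced breast MRI". It then plans sensitivity and specificity for each modality against biopsy and, if the data suffice, McNemar comparisons between CE-CBBCT and the other modalities. Tests are two-sided at the 95% confidence level.

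Section 5.7 times study imaging from the date of diagnostic mammography, so every subject has that test. Section 8 collects MRI and ultrasound only where they exist. The sole endpoint, in Section 3, is enrolment of up to 100 evaluable patients including 30 pathology-confirmed cancers.

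**The concern.** The masking rule names two tests that some women will not have and omits the one that all of them have. A reader could follow Section 6.3.3 to the letter with the mammographic work-up on the screen at the first decision. The CE-CBBCT result would then partly contain its comparator, and Section 9 would no longer compare CE-CBBCT with mammography.

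The direction is not fixed. A reader may add mammographic findings to the CE-CBBCT call, which raises sensitivity and lowers specificity. A reader may equally defer to a negative mammogram, which does the reverse.

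An analysis plan cannot repair this afterwards, because what a reader had already seen at the first decision cannot be undone. The first two questions that end Section 6.3.3 (lesions that other modalities missed, and separation of benign from malignant masses) are exposed in the same way if they are answered from the first decision.

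**Working it through.** **Text check**

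| Place | Mammography at the first decision | Histology at the first decision |
|---|---|---|
| 6.3.3, opening sentence | Available, no exception | Available, no exception |
| 6.3.3, step one | Not named in the mask | Not named in the mask |
| 6.3.3, later steps | Compared in step two | Compared in step three |
| 6.1 | Compared with the CBBCT images, no order given | Final confirmation after biopsy or surgery |

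MRI and ultrasound appear in the same step-two list as mammography, yet the authors still masked them by name in step one. Order of comparison alone was therefore not treated as masking. No section masks the first decision to mammography.

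**What one changed call is worth**

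The protocol gives no accuracy, between-modality agreement or reader influence, so there is no stated figure to reproduce. From the planned counts:

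- 30 cancers: one changed call moves sensitivity by 1/30 = 3.3 points.
- At most 100 − 30 = 70 non-cancers: one changed call moves specificity by at least 1/70 = 1.4 points. The step is larger if only biopsied women are scored.

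**Illustration (every input here is an assumption)**

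Both modalities have true sensitivity 80% and specificity 80%, so the true difference is zero. Let d be the probability of each discordant cell (CE-CBBCT positive with mammogram negative, and the reverse). Let k be the share of the relevant disagreements that are changed to match the mammogram.

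- Adding positive mammogram findings: sensitivity = 0.80 + dk; specificity = 0.80 − dk.
- Deferring to a negative mammogram: sensitivity = 0.80 − dk; specificity = 0.80 + dk.

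With independent errors, d = 0.80 × 0.20 = 0.16. Two x-ray tests of the same lesion probably err together, which makes d smaller, so d = 0.08 is shown as well. The McNemar column is the exact two-sided test on N = 30 cancers, enumerated over all trinomial outcomes with cell probabilities d and d(1 − k).

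| d | k | Sensitivity, adding | Sensitivity, deferring | Expected discordant cancers, adding | P(p<0.05) |
|---|---|---|---|---|---|
| 0.16 | 0 | 80% | 80% | 4.8 v 4.8 | 2.2% |
| 0.16 | 25% | 84% | 76% | 4.8 v 3.6 | 3.0% |
| 0.16 | 50% | 88% | 72% | 4.8 v 2.4 | 6.5% |
| 0.16 | 100% | 96% | 64% | 4.8 v 0 | 34.5% |
| 0.08 | 0 | 80% | 80% | 2.4 v 2.4 | 0.8% |
| 0.08 | 25% | 82% | 78% | 2.4 v 1.8 | 0.8% |
| 0.08 | 50% | 84% | 76% | 2.4 v 1.2 | 1.1% |
| 0.08 | 100% | 88% | 72% | 2.4 v 0 | 2.9% |

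Specificity moves by the same amount in the opposite direction. The test seldom reacts because the smallest significant one-way split is 6 v 0 (p = 2 × 0.5⁶ = 0.031); 5 v 0 gives p = 0.0625.

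Range over true sensitivity s at k = 50% with independent errors, where d = s(1 − s):

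- Adding: 0.70 + 0.21 × 0.5 = 80.5%, up to 0.90 + 0.09 × 0.5 = 94.5%.
- Deferring: 0.70 − 0.105 = 59.5%, up to 0.90 − 0.045 = 85.5%.

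**The case against.** **The order already covers it.** A CE-CBBCT decision is made first and mammography is compared next, so the natural reading is that the mammogram is opened at step two. This stands in part. A mammogram-free first read is plausible, and the text nowhere says that the mammogram is shown at step one. A reader might infer that the protocol directs an unmasked read; it does not. But the order does not secure masking, because MRI and ultrasound in the same list needed an express mask and the opening sentence points the other way.

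**Access to mammograms may be intended.** The aim given in Section 6.3.3 is the added value of CE-CBBCT, and the Synopsis makes CE-CBBCT with 2-view mammograms the test condition of the separate multi-reader study. This is possible. Section 9, however, scores the modalities one by one, so a combined read would need its own name there.

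**The link to Section 9 is inferred.** This stands. The protocol does not say which reads enter the accuracy analyses or how two readers are combined, and the case report forms and any analysis plan are not at hand. The point is therefore conditional on first reads being used. Which reads enter could be settled later; the conditions of reading could not.

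**The illustration sits high under independent errors.** This stands, and it is why d = 0.08 is shown beside d = 0.16.

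**A locked read may not mask a reader who knows the patient.** Section 16 allows radiologist investigators to recruit face to face. Whether they are the same two readers is not settled, so this is a limit on the fix.

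**Conclusion.** The point holds as an ambiguity with a possible consequence. The first CE-CBBCT decision is expressly masked to MRI and ultrasound only, and the opening sentence of Section 6.3.3 conflicts with a staged read for both mammography and histology. If first reads feed the conditional comparisons in Section 9, those comparisons are open to review bias.

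Neither the size nor the sign can be derived from the protocol. On the stated assumptions with half of the relevant disagreements changed, sensitivity shifts by 4 to 8 points in either direction. When positive mammogram findings are added, the chance of p<0.05 is 1.1% to 6.5%. The main harm is to the estimates, not to the test.

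Two stronger readings are not supported. One is that the bias favours CE-CBBCT; deferring to negative mammograms would lower its sensitivity. The other is that the trial's main result or the pivotal claim is compromised. The only endpoint is enrolment, and the pivotal comparison belongs to a separate multi-reader study. Neither depends on these reads. This is a cheap improvement.

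**What to change.** - In step one of Section 6.3.3, have each reader record and lock the CE-CBBCT decision before seeing the diagnostic mammography work-up and its BIRADS category, MRI, ultrasound or histology.
- If the 2-view mammograms are meant to be visible at step one, say so, and name the index test CE-CBBCT+2-view mammograms in Section 9.
- State that only the locked first reads enter the sensitivity, specificity and McNemar comparisons in Section 9.
- Reword the opening sentence of Section 6.3.3 and the reading sentence in Section 6.1 to match the three steps. The later comparison with other modalities stays as it is.
- Where a reader took part in a subject's recruitment or work-up, assign the case to the other reader if possible, and otherwise report it as a limit.
- Report the limit that remains in any case: readers know that the scan is of the breast of interest (Section 6.2.2: "A unilateral 3D CE-CBBCT for breast imaging study will be performed") in a woman with a detected abnormality (Section 5.7).

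The cost is a wording change and a fixed reading order, with no added procedure for subjects. Reads must be sequenced and locked, and apparent accuracy may move either way.
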